1. AMENDMENT HISTORY

Protocol v4.1 Non Substantial Amendment/NDA, UVRI REC, UNCST and OxTREC Resubmission

Section	From	Changed To
3.3	
Schedule of visits and procedures for groups 5 and 6
 
Timelines (days): Screening, 0, 2, 14, 28, 56-140, 63-147, 84-168, 140-224, 224-308
 
Timeline (weeks): 0, 2, 4, 8-20, 9-21, 12-24, 20-32, 32-44
	
Schedule of visits and procedures for groups 5 and 6
 
Timelines (days): Screening, 0, 2, 14, 28, 56-365, 63-372, 84-393, 140-449, 224-533
 
Timeline (weeks): 0, 2, 4, 8-52, 9-53, 12-56, 20-64, 32-76

7.9	
Follow up period
 
The follow up period for those enrolled after the COVID 19 lockdown will be 24 weeks after first vaccination and 24 weeks after booster vaccination for those enrolled before the lockdown in accordance with findings from previous studies in which adequate safety data and reliable markers of immunogenicity have been obtained in this time interval. Due to the nearly three months COVID-19 lockdown and halting of trial activities, participants who had already been enrolled in the trial by that time will have a later MVA85A vaccination boost ranging of up to 20 weeks (instead of 8 weeks) after initial vaccination with ChAdox1 85A. Their subsequent follow up visits will be at day 7, day 28, 3 months and 6 months post boost vaccination. Their follow up visits will therefore fall within the following ranges of 63-147, 84-168, 140-224 and 224-308 days.
	
Follow up period
 
The follow up period for those enrolled after the COVID 19 lockdown will be 24 weeks after first vaccination and 24 weeks after booster vaccination for those enrolled before the lockdown in accordance with findings from previous studies in which adequate safety data and reliable markers of immunogenicity have been obtained in this time interval. Due to the nearly three months COVID-19 lockdown and halting of trial activities, participants who had already been enrolled in the trial by that time will have a later MVA85A vaccination boost ranging of up to 52 weeks (instead of 8 weeks) after initial vaccination with ChAdox1 85A. Their subsequent follow up visits will be at day 7, day 28, 3 months and 6 months post boost vaccination. Their follow up visits will therefore fall within the following ranges of 63-372, 84-393, 140-449 and 224-533 days.

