6. OBJECTIVES AND OUTCOME MEASURES

Objectives	Outcome Measures	Timepoint(s) of evaluation of this outcome measure
Primary Objective To evaluate the safety and immunogenicity of ChAdOx1 85A – MVA85A prime-boost vaccination in Ugandan adolescents	Actively and passively collected data on adverse events	All Adverse Events (AEs) from day 0-28 post vaccination Serious Adverse Events (SAEs) throughout follow up
	T-cell Interferon- γ ELIspot response to antigen 85A	ELIspot spot-forming counts per 1×10^6 peripheral blood mononuclear cells (PBMCs) at day 14 for groups 1-4 ELIspot spot-forming counts per 1×10^6 peripheral blood mononuclear cells (PBMCs) at day 63 for groups 5 and 6 Area under the curve (AUC) analysis of immunogenicity (days 0-168 for groups 1-4; days 0-168 for groups 5 and 6)
Secondary Objective To further characterise immunogenicity of ChAdOx1 85A – MVA85A prime-boost vaccination in Ugandan adolescents	Antibody response to antigen 85A Exploratory immunology including ELIspot response to BCG, flow cytometry, gene expression, and mycobacterial killing assays	Screening and follow up visits as shown in Schedule of Visits, section 3
Tertiary Objectives 
 
To compare the response to ChAdOx1 85A – MVA85A prime-boost vaccination with the response to BCG revaccination in Ugandan adolescents 
To compare the response to ChAdOx1 85A – MVA85A prime-boost vaccination in Ugandan adolescents with the response in Oxford adults 
To investigate pre-immunisation epidemiological and immunological characteristics associated with the immune response induced by ChAdOx1 85A – MVA85A prime-boost vaccination in Ugandan adolescents 	T-cell Interferon- γ ELIspot response to antigen 85A Antibody response to antigen 85A, exploratory immunology including T cell ELIspots, flow cytometry, gene expression, and mycobacterial killing assays	Primary outcomes for these analyses will be antigen 85A specific ELIspot spot-forming counts per 1×10^6 peripheral blood mononuclear cells (PBMCs) at day 63 from the first vaccination and ELIspot AUC analysis Additional outcomes using data from follow up visits as shown in Schedule of Visits, section 3 Screening and follow up visits as shown in Schedule of Visits, section 3

Table 4. Objectives and Outcome Measures

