7. TRIAL DESIGN

We will commence with a dose-escalation and age de-escalation study in healthy adults and adolescents in Uganda, focussing on ChAdOx1 85A, to provide safety data for ChAdOx1 85A in this population. These measures are not required for MVA85A since this vaccine has been more widely used, including among adolescents in Uganda, and the dose has been standardised (as described above).

ChAdOx1 85A dose escalation and age de-escalation will be followed by a Phase IIa randomised trial comparing the immunogenicity of ChAdOx1 85A and MVA85A with the immunogenicity of BCG revaccination. ChAdOx1 85A and MVA85A will be administered via the intramuscular route. The target dose for the Phase IIa trial is 2.5×10^{10} vp because the lower dose is expected to have lower immunogenicity, based on the Oxford study, TB034 (Table 3, above). Data from the Oxford study suggest that this dose will be well tolerated. However, if this dose is not tolerated then the lower dose will be used. The dose of MVA85A will be 1×10^8 pfu in the groups in which it is given.

There will be 6 study groups with 3 to 30 volunteers in each group (Table 5).

Dose escalation for ChAdOx1 85A in adults

Group 1. The first three adults will receive ChAdOx1 85A at 5×10^9 vp.

Group 2. The next three adults will be enrolled after safety data has been reviewed by the trial management team to one week after ChAdOx1 85A vaccination in group 1. These adults will receive ChAdOx1 85A at 2.5×10^{10} vp.

Age de-escalation and dose escalation for ChAdOx1 85A in adolescents

Group 3. The first three adolescents will be enrolled after safety data has been reviewed to one week after ChAdOx1 85A vaccination in group 2. These three adolescents will receive ChAdOx1 85A at 5×10^9 vp

Group 4. The next three adolescents will be enrolled after safety data has been reviewed to one week after ChAdOx1 85A vaccination in group 2. These three adolescents will receive ChAdOx1 85A at 2.5×10^{10} vp

Randomised comparison of ChAdOx1 85A-MVA85A versus BCG revaccination

Once safety data has been reviewed for groups 1 to 4 to one week post ChAdOx1.85A vaccination, recruitment to the randomised trial will commence. Sixty adolescents will be randomised, 30 (group 5) to receive ChAdOx1 85A at 2.5×10^{10} vp followed by MVA85A boost and 30 (group 6) to receive BCG revaccination.

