7.2. Recruitment

The Entebbe Mother and Baby Study.

This project will be undertaken within the Entebbe Mother and Baby Study (EMaBS) cohort [56]. Between 2003 and 2005, 2,507 pregnant women were recruited to the cohort at the antenatal clinic of Entebbe General Hospital, Uganda. The study area was Entebbe Municipality and the neighbouring Katabi sub-county. The original objective was to investigate the effects of prenatal exposure to helminth infection on the infant response to vaccines, and on infant susceptibility to infectious diseases [56]. Children were born between April 2003 and April 2006. In 2018, they will be aged 12 to 17 years. The cohort has unique value for this study because extensive data are available on factors relevant to this trial including date of birth, date and strain of infant BCG immunisation, immune responses to TB antigens at age one and five years, and exposure to infectious diseases including TB, malaria, helminths and viral infections. Genetic data are also available for this cohort. Field workers regularly visit the participants at home and record the location of the home by global positioning systems (GPS) in order to facilitate follow up, and to allow adjustment for potential confounding related to location of residence in the analysis of results. The EMaBS archived data will contribute to investigation of factors that impact vaccine immunogenicity (tertiary aim 3).

Stakeholder engagement.

Before initiating the study, we will hold a series of meetings to engage relevant stakeholders, including vaccine and tuberculosis programmes at the Ministry of Health, district health officials, local council leaders and hospital staff. Also, we will hold meetings for community representatives, and for EMaBS participants and their families. The proposed work will be explained, and questions about it will be addressed. A consultative group of selected parents will be set up; this group will advise us on issues such as the timing of activities in relation to the school year.

Recruitment of volunteers

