11. STATISTICS

This is primarily an exploratory immunogenicity and safety trial with descriptive endpoints.

Adverse events will be listed and summarised by type of AE, frequency, severity and trial group.

The sample size (12 participants for dose escalation and age de-escalation, 60 participants [30 in each arm] for the randomised trial) has been determined by the number of doses of ChAdOx1 85A available for this study. The following are the considerations regarding sample size for the randomised component of the trial. The primary outcome is the IFN- γ ELIspot response to antigen 85A at week 9 which is measured in spot forming counts per 1×10^6 peripheral blood mononuclear cells (PBMCs). Assuming a standard deviation of $0.4 \log_{10}$ sfc/ 1×10^6 PBMC (spot forming counts/ 1×10^6 peripheral blood mononuclear cells) in the peak Ag85A response, our study will have over 80% power to detect a difference of $0.29 \log_{10}$ in sfc/ 10^6 PBMC with $p < 0.05$. This is comparable to the difference that was observed between the response to human adenovirus vectored TB vaccine candidate Aeras 402 alone (Day 14 post Aeras) and Aeras 402 with MVA85A boost (Day 7 post MVA boost) [21], or between BCG (Day 28) and MVA85A alone (Day 7) in UK subjects [62], and hence a reasonable difference to expect between BCG and ChAdOx1 85A-MVA85A (aim 2).

For outcomes that are approximately normally distributed or normalised by log-transformation, differences in means will be presented together with 95% confidence intervals and p-values from unpaired t-tests. For non-normally distributed outcomes, the difference in medians between the two groups will be presented along with its 95% confidence intervals, and p-values from Wilcoxon ranksum tests.

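### Tertiary objective 3 looks for predictors of the prime-boost response in group 5 without accounting for a prime-boost interval of 8 to 52 weeks, and its named outcomes are still timed from the first vaccination

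*Combined protocol and SAP*

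**What the plan says.** Table 4 (Section 6) gives tertiary objective 3 as "To investigate pre-immunisation epidemiological and immunological characteristics associated with the immune response" induced by the prime-boost regimen. For the tertiary analyses it names the Ag85A ELISpot count "at day 63 from the first vaccination and ELIspot AUC analysis" as primary outcomes, and it defines the AUC for groups 5 and 6 over days 0-168. Only group 5 receives both vaccines (Section 7: "Sixty adolescents will be randomised, 30 (group 5) to receive" the prime and boost).

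The v4.1 entry for Section 7.9 states that "participants who had already been enrolled in the trial by that time will have a later MVA85A vaccination boost ranging of up to 52 weeks". The current Section 7.9 carries the same rule and keeps day 56 for new enrollees. Section 8.4.2 on the booster and the footnote to Table 1.2 agree that timing depends on enrolment before or after the lockdown. Section 8.4.3 still gives day 140 as the upper limit and has to be reconciled with these.

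Section 11 describes comparisons of two groups: "differences in means will be presented together with 95% confidence intervals and p-values from unpaired t-tests", or rank-sum tests. It gives no model for objective 3, and the v4.0 and v4.1 change tables do not list it. The only adjustment named anywhere is in Section 7.2, where home locations are recorded "to allow adjustment for potential confounding related to location of residence in the analysis of results".

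**The concern.** Randomisation protects the comparison of group 5 with group 6. It does not protect a search for predictors inside group 5. There, the time between prime and boost now depends on when a participant enrolled. This causes two problems.

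First, outcomes timed from day 0 capture a different amount of post-boost response in different participants, whatever the biology.

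Second, if the interval affects the response, a characteristic that drifts with enrolment date can look like a predictor when it is not, or a real predictor can be hidden. Age at prime drifts in this way because all adolescents come from one birth cohort (Section 7.2: "Children were born between April 2003 and April 2006"). Helminth infection and sub-microscopic malaria at screening may also vary over time. What is at stake is the reading of an exploratory predictor analysis, not the primary result.

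**Working it through.** **1. The plan's own figure.** Section 11 gives SD 0.4 log10, difference 0.29 log10, 30 per arm and over 80% power. By normal approximation, (0.29/0.4) x sqrt(30/2) - 1.96 = 2.81 - 1.96 = 0.85, giving power of 0.802; a t-test gives 0.788. The figure reproduces to within 2 points, but it concerns the randomised comparison. No figure is given for objective 3.

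**2. Outcomes timed from day 0.** Post-boost days inside the day 0-168 window = max(0, 168 - boost day):

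| Boost day | Post-boost days in AUC |
|---|---|
| 56 | 112 |
| 140 | 28 |
| 168 or later | 0 |

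Section 5.1.5 reports that MVA85A significantly raised the response in the UK phase I trial, so this AUC depends on the interval by construction. Likewise, day 63 read literally falls before the boost for anyone boosted after day 63. The schedule itself does not have this defect: it places visits at 63-56 = 7, 84-56 = 28, 140-56 = 84 and 224-56 = 168 days after the boost, and the upper limits give the same gaps (372, 393, 449 and 533, each minus 365).

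**3. Link between age at prime and delay, if every pre-lockdown participant is delayed.** Assume births are uniform over three years and independent of enrolment order, so s = 3/sqrt(12) = 0.866 years. Let p be the fraction delayed and g the gap in mean enrolment date, in years. In absolute value:

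correlation = g x sqrt(p(1-p)) / sqrt(s^2 + g^2 x p(1-p))

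- g = 1, p = 0.5: 0.5/sqrt(0.75 + 0.25) = 0.50.
- g = 0.25, p = 0.5: 0.125/sqrt(0.75 + 0.0156) = 0.14.

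If a long interval shifts the response by 0.29 log10 (assumed), the spurious age slope is 0.29 x g x p(1-p)/(s^2 + g^2 x p(1-p)). At g = 1 and p = 0.5 this is 0.29 x 0.25/1.00 = 0.07 log10 per year. Simulated tests of age with no true effect (n = 30, SD 0.4, half delayed, 4,000 runs) reject at the 5% level as follows:

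| Shift | Gap 0.25 y | Gap 1 y | Gap 1.5 y |
|---|---|---|---|
| 0 | 5% | 5% | 5% |
| 0.15 log10 | 5% | 9% | 10% |
| 0.29 log10 | 6% | 15% | 22% |

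A delayed-boost term in the model returns every cell to between 4.5% and 5.5%.

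**4. The same test if only late pre-lockdown enrollees are delayed.** Before v4.0 the boost was due at day 56 with a 5-day window, so anyone primed more than 56 + 5 = 61 days before the halt could have been boosted on time. Assume half of group 5 enrolled before lockdown, enrolment restarted 3 to 6 months after lockdown began, and later enrolment ran for 6 months. For shifts of 0.2 to 0.4 log10:

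- Pre-lockdown enrolment over 6 to 12 months: correlation -0.03 to -0.15, rejection rate about 4-7%.
- Pre-lockdown enrolment over 3 months: correlation -0.20 to -0.29, rejection rate about 5-12%.

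In this pattern, day-56 boosts lie on both sides of the delayed group, which weakens the link with age.

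**The case against.** The case on the other side has five parts.

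- **Evidence of an interval effect.** Section 5.1.5 reports no difference one week after MVA85A between boosts at day 56 and day 119 (p = 0.31). This stands as a caution, but it does not exclude an effect: there were 12 per group, the groups differed in the number of primes, and 119 days is far short of 365. It also does not bear on the AUC, where the dependence is arithmetic.
- **Randomised approach list.** A reader might infer that any trait is exposed. Section 7.2 does not support that. Eligible participants are approached in randomised order, so birth date, sex, genetics and archived early-life data should be broadly unrelated to enrolment date. Microscopy-positive malaria at screening is an exclusion. Age at prime and time-varying traits remain.
- **Size.** A reader might infer that a false-positive rate of 14-22% is the expected result. That needs the whole pre-lockdown cohort delayed and a gap of a year or more. The documents give neither the number delayed nor the gap, and other plausible patterns show no visible inflation.
- **No commitment to an unadjusted analysis.** Section 11's tests are for two groups and are not assigned to objective 3. This is correct: the plan is silent on the model, and an analyst could still adjust. But nothing directs that adjustment, and silence does not correct the outcome definitions.
- **Day 63 as a visit label.** Day 63 could be read as visit 7, which the schedule moves to 7 days after the boost. On that reading the day-63 outcome is sound, but Table 4 says it is counted from the first vaccination, and the AUC window is unaffected.

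**Conclusion.** The concern holds in a limited form. In group 5 the interval runs from 8 to 52 weeks according to enrolment period, the plan does not account for it in objective 3, and two named outcomes remain timed from the first vaccination. For the AUC, and for day 63 read literally, the interval is built into the outcome. This rests on the plan's own figures and on the reported boosting effect of MVA85A.

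Confounding of age at prime and time-varying screening traits is possible but not established. It requires an interval effect, which the documents do not show, and an enrolment pattern that they do not describe. With an assumed shift of 0.2 to 0.4 log10, the false-positive rate for age lies between about 5% and over 20%. The documents do not support one figure within that range, nor a claim that traits fixed at birth are biased. The objective is tertiary and exploratory, and the randomised comparison is not confounded by enrolment date.

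**What to change.** In Section 11 and in Table 4 under tertiary objective 3:

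1. Define the outcomes relative to the actual boost: log10 Ag85A ELISpot count 7 days post-boost, and an AUC over a fixed post-boost window. The existing visits at 7, 28, 84 and 168 days post-boost supply the points.
2. Estimate associations by linear regression on log10 counts, with log(actual prime-boost interval in days) in every model. A before/after-lockdown indicator alone is not enough, because it pools day-56 with day-365 boosts among those enrolled early. A covariate without step 1 is not enough either, because it cannot repair an outcome measured before the boost.
3. Repeat the analysis in participants boosted at day 56, within the visit window, as a sensitivity analysis.
4. Report the number delayed and the distribution of intervals and enrolment dates, so that readers can judge the possible bias.

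The main model loses one degree of freedom out of 30, and the sensitivity analysis loses precision through its smaller sample. No new data are needed if actual vaccination dates are recorded, as the schedule's use of actual visit dates implies. The change should be written down before the predictor analysis begins, so that the covariates are not chosen after seeing the results.

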3. SYNOPSIS

3.1. Trial Synopsis

Trial Title	Open label, dose escalation and age de-escalation for ChAdOx1 85A, followed by a Phase IIa randomised, open-label trial among adolescents comparing ChAdOx1 85A prime followed by MVA85A boost versus BCG re-vaccination			
Trial Identifier	TB042			
Trial Centres	MRC/UVRI and LSHTM Uganda Research Unit [name] [contact] [contact]			
Clinical Phase	Phase IIa			
Design	Open label, dose escalation and age de-escalation for ChAdOx1 85A followed by a randomised, open-label trial among adolescents, comparing ChAdOx1 85A prime followed by MVA85A boost versus BCG re-vaccination			
Trial participants	Adolescents participating in the Entebbe Mother and Baby Study (EMaBS) birth cohort and their parents			
Planned Sample Size	Total: 72 healthy, previously BCG-vaccinated volunteers receiving either ChAdOx1 85A intramuscularly at different doses, or a prime-boost regimen of ChAdOx1 85A intramuscularly followed by MVA85A intramuscularly, or BCG re-vaccination intradermally.			

Dose escalation in adults
 
Group 1: 3 adults who are parents of EMaBS participants, to receive ChAdOx1 85A at 5×10^9 vp
 
Group 2: 3 adults who are parents of EMaBS participants, to receive ChAdOx1 85A at 2.5×10^{10} vp
				

Age de-escalation and dose escalation in adolescents
 
Group 3: 3 adolescents who are EMaBS participants, to receive ChAdOx1 85A at 5×10^9 vp
 
Group 4: 3 adolescents who are EMaBS participants, to receive ChAdOx1 85A at 2.5×10^{10} vp
				

Randomised comparison of ChAdOx1 85A-MVA85A versus BCG revaccination
 
Group 5: 30 adolescents who are EMaBS participants, to receive ChAdOx1 85A at 2.5×10^{10} vp followed by MVA85A boost
 
Group 6: 30 adolescents who are EMaBS participants, to receive BCG revaccination
				
Vaccination Schedule	ChAdOx1 85A or BCG revaccination on day zero; where applicable MVA85A on day 56			
Follow-up Duration	24 weeks after vaccination for groups 1-4; one year after first vaccination for groups 5 and 6			
Trial Interventions	Intramuscular or intradermal vaccination Venepuncture			
Trial Duration	Estimated 30 months			
Planned Trial Period	Prospective start date for enrolment 01.02.2018			
Primary	Objectives	Outcome Measures		
	To evaluate the safety and immunogenicity of ChAdOx1 85A – MVA85A prime-boost vaccination in Ugandan adolescents	Actively and passively collected data on adverse events T-cell Interferon- γ ELISPOT response to antigen 85A and PPD		

Secondary	To further characterise immunogenicity of ChAdOx1 85A – MVA85A prime-boost vaccination in Ugandan adolescents	Antibody response to antigen 85A and PPD; exploratory immunology including flow cytometry, gene expression, and mycobacterial growth inhibition assays
Tertiary	
 1. To compare the response to ChAdOx1 85A – MVA85A prime-boost vaccination with the response to BCG revaccination in Ugandan adolescents 2. To compare the response to ChAdOx1 85A – MVA85A prime-boost vaccination in Ugandan adolescents with the response in Oxford adults 3. To investigate pre-immunisation epidemiological and immunological characteristics associated with the immune response induced by ChAdOx1 85A – MVA85A prime-boost vaccination in Ugandan adolescents 	
T-cell Interferon-γ ELispot response to antigen 85A and PPD
 
Antibody response to antigen 85A and PPD; exploratory immunology including flow cytometry, gene expression, and mycobacterial growth inhibition assays

Investigational products	Investigational products: ChAdOx1 85A, MVA85A Comparator: Bacille Calmette Guerin (BCG); strain in use in Uganda at the time of the trial	
Dose(s)	ChAdOx1 85A: 5×10^9 vp and 2.5×10^{10} vp MVA85A: 1×10^8 pfu BCG: 0.1 ml	
Route of administration	ChAdOx1 85A: intramuscular needle injection in the deltoid region of the arm MVA85A: intramuscular needle injection in the deltoid region of the arm BCG: intradermal needle injection in the deltoid region of the arm	
Allocation Method	
Group 1: the first three adults will receive ChAdOx1 85A at 5×10^9 vp
 
Group 2: the next three adults will receive ChAdOx1 85A at 2.5×10^{10} vp
 
Group 3: the first three adolescents will receive ChAdOx1 85A at 5×10^9 vp
 
Group 4: the next three adolescents will receive ChAdOx1 85A at 2.5×10^{10} vp
 
Thereafter, 60 adolescents will be randomised, 30 (group 5) to receive ChAdOx1 85A at 2.5×10^{10} vp followed by MVA85A boost and 30 (group 6) to receive BCG revaccination
	

